6.6. Safety Summaries and Analyses

The safety analysis set is the primary population for the safety summaries and analyses.

Safety will be summarized Overall, and separately for Period A and Period B for data that is not presented by time point (eg, AEs, concomitant medications, Lab/VIS/ECG categorical determinations).

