### 5.5.3. Period B: Maintenance

After the Week 10 Visit (primary endpoint collection), subjects will enter Period B. During Period B, double-blind treatment with investigational product will continue as adjunctive treatment to a stable dose of open label L-Dopa.

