2.2. Study Design

The study has a randomized, double-blind, placebo-controlled parallel group design. Approximately 198 subjects from approximately 60 centers in approximately 6 countries will be randomized to 5 treatment groups (15 mg QD, 7 mg QD, 3 mg QD, 1 mg QD, or placebo), initially in a 2:0:0:0:1 ratio of approximately 54 subjects (Cohort 1) followed by a 1:2:2:2:1 ratio of approximately 144 subjects (Cohort 2), using a central randomization system with randomization blocks stratified by region. Geographic region will be defined as North America, Japan, and Europe.

[figure not shown]
Each subject will participate in the study for approximately 25 weeks including up to a 45 day screening period, 15 week double-blind treatment period (comprising up to a 3 week titration, 2 week dose adjustment, 5 weeks of primary efficacy with adjunctive treatment to stable L-Dopa (Period A), and 5 weeks of maintenance with adjunctive treatment to stable L-Dopa (Period B)), and an approximately 28 day follow-up period.

Note that prior to B7601003 Protocol Amendment 2 Days 14 and 21 were required in-clinic visits, but now with the option to be phone visits, as applicable. The impact of this change will be noted in subsequent sections.

For sites in Japan, the Week 2 (Day 14) and Week 3 (Day 21) visits during the Titration Period must be conducted as site (in-clinic) visits. Additionally, two additional phone visits are required a day after both the Day 0 (Randomization) Visit (Day 1) and Week 1 Visit (Day 7 [+3 day window]) and two additional study site visits are required a day after both Week 2 Visit (Day 14 [+3 day window]) and Week 3 Visit (21 [+3 day window]), ie Day 15 and Day 22 respectfully. Phone visits can optionally be conducted as site visits (eg, for logistical reasons).

The study design is illustrated in the figure below.

Figure 1. Study Schematic

Each subject is planned to be up-titrated in a double-blind fashion to the assigned target dose level of PF-06649751 or placebo according to the following titration scheme:

Table 2. Proposed Titration Schemes for PF-06649751 and Placebo Doses

Week/ Start Day of Dose Level	Treatment Group				
	Placebo	1 mg	3 mg	7 mg	15 mg
Week 1 / from Day 1	P	1 mg	1 mg	1 mg	1 mg
Week 2/ from Day 8	P	1 mg	3 mg	3 mg	3 mg
Week 3 / from Day 15	P	1 mg	3 mg	7 mg	7 mg
Weeks 4-15 / from Day 22	P	1 mg	3 mg	7 mg	15 mg

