Titration (Week 1 to Week 3): *No modifications to the upward titration of Study Medication can be made. Subjects who experience intolerable adverse events during titration will need to be discontinued from the study.*

Post Week 3 (Week 4 to Week 5): *For subjects who experience unacceptable new adverse events after having achieved the target dose (after Day 21) and deemed related to the dose increase, the dose of investigational product can be changed to the previous dose level (Week 3 dose level). This results in a dose reduction from 15 mg/day to 7 mg/day for the highest dose group, and no change in dose for the other dose groups in a blinded fashion. Only one dose modification of investigational product is permitted.*

L-Dopa Adjustment for Unacceptable Dopaminergic Side Effects (Week 1 to Week 15): *In the case of unacceptable dopaminergic side effects and following discussion with the Medical Monitor, the dose of L-Dopa may be reduced between Day 1 and Day 105 visit.*

Period A: Primary Efficacy: *During Period A, subjects will be administered double blind study medication once daily (up to 4 different dose levels of investigational product) as adjunctive treatment to a stable dose of open-label L-Dopa.*

Period B: Maintenance: *After the Week 10 Visit (primary endpoint collection), subjects will enter Period B. During Period B, double-blind treatment with investigational product will continue as adjunctive treatment to a stable dose of open label L-Dopa. Note that prior to B7601003 Protocol Amendment 2 Period B allowed the open label L-Dopa dose to be reduced following a recommended downward titration based on the L-Dopa dose at the end of Period A. The impact of this change will be noted in subsequent sections.*

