3.5.1. Adverse Events

An adverse event is considered treatment emergent relative to a given treatment if:

- the event occurs for the first time during the effective duration of treatment and was not seen prior to the start of treatment (for example, during the baseline or run-in period), or
- the event was seen prior to the start of treatment but increased in severity during treatment.

The effective duration of treatment is determined by the lag time. Any event occurring within the lag time, whether this occurs during a break in treatment or at the end of treatment, is attributed to the corresponding treatment period. An infinite lag will be used for the study.

A 3-tier approach will be used to summarize AEs. Under this approach, AEs are classified into 1 of 3 tiers. Different analyses will be performed for different tiers (See [Section 6.6.1](#)).

Tier-1 events: These are pre-specified events of clinical importance and are maintained in a list in the product's Safety Review Plan (no Target Medical Events {TMEs} have been defined at this point in time)

Tier-2 events: These are events that are not tier-1 but are "common". A MedDRA PT is defined as a Tier-2 event if there are 4 or more subjects with that PT in any treatment group, given the trial will have less than 400 or fewer subjects per treatment group ("Rule of 4").

Tier-3 events: These are events that are neither Tier-1 nor Tier-2 events. Pfizer standard safety output where all AEs will be included (ie, no new outputs).

Adverse Events will be determined Overall, and separately for Period A and Period B.

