6. ANALYSES AND SUMMARIES

Both the FAS and PPAS populations will be used in the analyses of the primary efficacy endpoint, with the FAS being primary. For all other efficacy endpoints, only the FAS analysis set will be utilized.

For all efficacy analyses and summaries (Sections 6.1, 6.2, 6.3 {except CCI [REDACTED]} and 6.4): All data collected for subjects consented under Protocol Amendment 2 prior to entering Period B will be included for modelling and summaries. Otherwise, only data collected through Week 10 (Period A) will be included for subjects who do not meet the above condition, and their data collected after Week 10 will be in listings only.

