6.5. Baseline and Other Summaries and Analyses

6.5.1. Study Conduct and Subject Disposition

Data will be reported in accordance with Pfizer Data Standards. Disposition will be further categorized by the treatment phase Titration, Dose Adjustment, Period A, Period B (may be separated by preA2 and A2), and Follow-up.

Overall subject disposition will include data through Double-Blind treatment period (study treatment period) and separately through Follow-up (overall study).

The number of subjects by region and country will be displayed.

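### Combined-cohort Period B safety tables do not separate subjects who entered Period B before consenting to Amendment 2, when an L-Dopa taper was allowed, so dose comparisons in them can be confounded with the taper

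*SAP*

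**What the plan says.** **The two L-Dopa regimens.** SAP 2.2 records, of the time before Amendment 2, that "Period B allowed the open label L-Dopa dose to be reduced following a recommended downward titration based on the L-Dopa dose". Under the current Protocol 5.5.3, "double-blind treatment with investigational product will continue as adjunctive treatment to a stable dose of open label L-Dopa".

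**Efficacy.** SAP 6 keeps the two apart. For subjects not consented under Amendment 2 before entering Period B, "their data collected after Week 10 will be in listings only". The rule names SAP 6.1 to 6.4 only, so 6.6 is outside it.

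**Safety.** SAP 3.5.1 says "Adverse Events will be determined Overall, and separately for Period A and Period B", and 3.5.2 to 3.5.4 say the same for laboratory, vital-sign and ECG abnormalities. SAP 6.6 repeats it: "Safety will be summarized Overall, and separately for Period A and Period B for data that is not presented by time point". SAP 6.6.1 compares each dose with placebo by risk difference with a 95% interval for Tier-1 and Tier-2 events. None of these sections excludes or splits pre-Amendment 2 subjects.

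**Where a split or related table does appear.** SAP 6.5.1 mentions one for disposition, as an option: "Period B (may be separated by preA2 and A2"). SAP 5.2 shows safety for both cohorts combined and also for each cohort. SAP 6.5.4 tabulates changes in background Parkinson's medication for Periods A and B, but leaves out L-Dopa.

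**Allocation.** Subjects are randomized "initially in a 2:0:0:0:1 ratio of approximately 54 subjects (Cohort 1) followed by a 1:2:2:2:1 ratio of approximately 144 subjects (Cohort 2"), in the order 15, 7, 3, 1 mg and placebo.

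**The concern.** The SAP regards the two versions of Period B as different enough to keep apart for efficacy, yet its safety tables pool them. Pooling alone would not bias a comparison of arms randomized concurrently in one fixed ratio. The difficulty is that the ratio changes between cohorts. The 1, 3 and 7 mg arms exist only in Cohort 2, while Cohort 1 supplies a large part of 15 mg and placebo. Protocol 1.5.2 places the dose-ranging part after the Cohort 1 interim analysis, so pre-Amendment 2 subjects are likely to sit mainly in those two arms.

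Reducing L-Dopa could plausibly lower some dopaminergic events and raise reports of worsening Parkinson's disease. In the combined table, a difference in Period B event rates between a low dose and placebo could then partly reflect how many placebo subjects were eligible for a taper. Safety and tolerability is a secondary objective, and tolerability bears on the therapeutic window in the primary objective. A reader of these tables would have no means of seeing the mixture, because the medication-change table omits L-Dopa.

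**Working it through.** **Inputs.** The cohort sizes and ratios are from SAP 2.2. The documents give no figure for Period B safety, nor the number of subjects who entered Period B before consenting to Amendment 2. Both that number and the taper effect are assumptions, shown as ranges.

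**Step 1: the plan's arm sizes.**
- Cohort 1, 54 at 2:1: 36 on 15 mg and 18 on placebo.
- Cohort 2, 144 at 1:2:2:2:1: 18 on 15 mg, 36 each on 7, 3 and 1 mg, and 18 on placebo.
- Totals: 54 on 15 mg and 36 in each other arm. 54 + 4 × 36 = 198, as stated.

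**Step 2: taper-eligible share per arm.** Let f be the share of Cohort 1 that entered Period B before consenting to Amendment 2, with none in Cohort 2.
- 15 mg: f × 36/54
- Placebo: f × 18/36
- 1, 3 and 7 mg: 0

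These use planned randomized numbers, so they assume that within each arm the two cohorts reach Period B in equal proportion.

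**Step 3: shift in the pooled risk difference.** Let x be the average change in Period B event risk among taper-eligible subjects. Then shift = x × (share in dose arm − share in placebo). This gives x × f/6 for 15 mg and −x × f/2 for each lower dose. With x = +10 points:

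| f | 15 mg share | Placebo share | Lower-dose share | Shift, 15 mg | Shift, 1, 3 and 7 mg |
|---|---|---|---|---|---|
| 0.25 | 16.7% | 12.5% | 0% | +0.4 | −1.25 |
| 0.5 | 33.3% | 25.0% | 0% | +0.8 | −2.5 |
| 1 | 66.7% | 50.0% | 0% | +1.7 | −5.0 |

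If the taper lowers an event by 10 points, every sign reverses.

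**Step 4: relax the Cohort 2 assumption.** With all of Cohort 1 and half of Cohort 2 pre-Amendment 2, the shares are (36 + 9)/54 = 83.3% for 15 mg, (18 + 9)/36 = 75% for placebo and 18/36 = 50% for each lower dose. The shifts fall to +0.8 and −2.5. If everyone or no one is pre-Amendment 2, both shifts are zero.

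**Step 5: split by consent status.** In the Amendment 2 stratum the taper-by-design share is 0% in every arm; in the other stratum it is 100% in every arm present. The difference in share between dose and placebo is then 0 in both. In the pooled table it is up to +16.7 percentage points for 15 mg and −50 for the lower doses.

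**The case against.** **By-cohort displays are planned (SAP 5.2).** This is the strongest reply. Within a cohort the arms are randomized concurrently, so their expected taper-eligible shares are equal. If all pre-Amendment 2 subjects are in Cohort 1, the Cohort 2 table contains no taper by design and the Cohort 1 table compares 15 mg with placebo on equal terms. This stands, and it covers much of the worst case. It does not cover the combined-cohort tables. Nor is cohort the same as amendment status: a Cohort 1 table may average over two L-Dopa regimens without showing it, and Cohort 2 alone plans only 18 subjects each on 15 mg and placebo.

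**The facts that fix the size are missing.** A reader might infer that all pre-Amendment 2 subjects are in Cohort 1 and that 1, 3 and 7 mg were wholly on stable L-Dopa. The documents establish neither. Protocol 1.5.2 suggests the order of the cohorts but not who had consented to what. The SAP 6 rule turns on consent before Period B, so someone randomized earlier may still count as an Amendment 2 subject. Protocol 5.5.1 allows L-Dopa reduction for side effects in any arm through Day 105. The earlier Period B allowed a taper; it does not follow that every subject had one.

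**The shifts are small against noise.** For illustration, take rates of 20% against 15% with 36 per arm: the 95% half-width is 1.96 × √(0.20 × 0.80/36 + 0.15 × 0.85/36) = 17.5 points, against a shift of at most 5. This is fair, although a systematic shift is not excused by a wide interval.

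**No decision rule uses these tables.** SAP 6.6.1 calls the safety analysis generally exploratory, and criteria C1 and C2 rest on Week 10 OFF time. This limits the importance of the point but does not answer it.

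**Conclusion.** The gap is real and limited. The combined-cohort Period B safety tables and risk differences mix two L-Dopa regimens that the SAP separates for efficacy, and the change in allocation between cohorts means the mix can differ by arm. Comparisons of 1, 3 and 7 mg with placebo are the most exposed; 15 mg is affected much less and in the opposite direction. Under the assumed 10-point taper effect, with a quarter to all of Cohort 1 and none of Cohort 2 pre-Amendment 2, the shifts are 1.25 to 5 points and 0.4 to 1.7 points. They are smaller if part of Cohort 2 was also pre-Amendment 2, and zero if nobody was.

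A reader might infer that Period B safety by dose is confounded as a matter of fact, or that the tables would show a false inverse dose trend. The documents support neither. They do not give the number of affected subjects, any trend depends on an assumed event rate and on whether the taper raises or lowers a given event, and the by-cohort tables are free of this imbalance in expectation. The primary efficacy analysis at Week 10 is unaffected.

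**What to change.** 1. In SAP 3.5.1 to 3.5.4 and 6.6, present Period B safety summaries and risk differences separately by the consent flag of SAP 6: Amendment 2 consent before entering Period B, or not. If the second group proves confined to Cohort 1, show it as 15 mg against placebo only.
2. Add a summary by arm of L-Dopa dose change during Period B, since SAP 6.5.4 omits L-Dopa.
3. Keep the tables covering the whole treatment period on all treated subjects, with a footnote stating that Period B was conducted under two L-Dopa regimens. Do not censor pre-Amendment 2 subjects at Week 10 in those tables. That would shorten follow-up mainly in 15 mg and placebo while the lower doses kept 15 weeks, so incidence would be compared over unequal exposure.
4. Reconcile Protocol 5.5.3, which describes a stable L-Dopa dose in Period B, with the Day 70 procedures in Protocol 6.2.10, which still include an instruction to begin an L-Dopa down-titration. The meaning of the Amendment 2 stratum depends on this.

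The cost is SAP wording, one additional set of tables using a flag that efficacy already requires, and smaller Period B counts for 15 mg and placebo. The split removes the taper-by-design imbalance. It does not address any other difference between the cohorts, so the by-cohort displays should stay.

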6.6.1. Adverse Events

Adverse events will be listed and summarized within treatment group in accordance with the Pfizer Data Standards.

The details of Tier-1, Tier-2 and Tier-3 AEs are described in [Section 3.5.1](#).

Adverse events within Tier-1 and -2 will be summarized using Risk Differences between each PF-06649751 group and placebo, together with 95% CI. A graphical presentation of the percentage of subjects with each AE and Risk Difference (with 95% CI) ordered by decreasing risk difference will be shown for the Tier-1 and -2 AEs separately. Significance tests will be performed for the Tier-1 adverse events. There will be no multiplicity adjustment for these significance tests.

For Tier-1 and Tier-2 adverse event outputs, the following footnotes will be used: “P-values and confidence intervals are not adjusted for multiplicity and should be used for screening purpose only. The 95% Confidence intervals are provided to help gauge the precision of the estimates for Risk Difference. Risk Difference is computed as PF-06649751 1 mg versus Placebo, PF-06649751 3 mg versus Placebo, PF-06649751 7 mg versus Placebo, and PF-06649751 15 mg versus Placebo.”

Tier-1 events for risk difference and relative risk will use unconditional exact methods (an approach proposed by Chan and Zhang, 1999⁶) based on standardized statistics. For Tier-2 events, an asymptotic approach will be performed.

The Tier-3 adverse events will be described as part of the overall AE summary.

It should be recognized that most studies are not designed to reliably demonstrate a causal relationship between the use of a pharmaceutical product and an adverse event or a group of adverse events. Except for select events in unique situations, studies do not employ formal adjudication procedures for the purpose of event classification. As such, safety analysis is generally considered as an exploratory analysis and its purpose is to generate hypotheses for further investigation. The 3-tier approach facilitates this exploratory analysis.

6.6.2. Laboratory Data

Laboratory data will be listed and summarized within treatment group in accordance with the Pfizer Data Standards.

Incidence of laboratory test abnormalities (including without regard to baseline abnormality) will be summarized within each treatment group.

6.6.3. Vital Signs (Blood Pressure and Pulse Rate)

For each planned time point, baseline values and change from baseline values within each treatment will be summarized with descriptive statistics (using Pfizer Data Standards). A plot of individual blood pressure versus plasma concentration will be generated.

Maximum decrease and increase values and changes from baseline for vital signs (for supine and standing) will also be summarized descriptively within treatment group using categories as defined in the Pfizer Data Standards. Numbers and percentages of subjects meeting the categorical criteria will be provided. All planned and unplanned post-dose time points will be counted in these categorical summaries. All values meeting the criteria of potential clinical concern will be listed.

Vital signs collected at additional positions will be listed only.

The following non-standard safety tables will be included:

- A summary of postural change from supine to standing systolic and diastolic blood pressures.
- Incidence of subjects with orthostatic hypotension (defined in [Section 3.5.3](#) above), for each visit, last visit and any post-baseline incidence or orthostatic hypotension or minimum absolute change in postural blood pressure.

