#### B7601009

B7601009 (n=18) was a Phase 1b, double-blind, placebo-controlled, randomized, study to evaluate the safety, tolerability and pharmacokinetics of single ascending doses of PF-06649751 in Parkinson's disease subjects. Single doses of PF-06649751 0.75 mg, 1.5 mg, 3 mg, 6 mg, 9 mg were evaluated in the study.

Two (2) sequential cohorts were planned and were to be conducted over 3 treatment periods. Study drug or placebo was administered once during each of 3 treatment periods, with an at least 7 day study drug wash out phase between treatment periods.

Single doses of PF-06649751 up to 9 mg were safe and well tolerated by subjects with Parkinson's disease. There were no deaths, SAEs, severe AEs, discontinuations due to AEs, dose reductions or temporary discontinuation due to AEs. The most common mild to moderate AEs were headache, nausea, and vomiting. Nausea and vomiting appeared to be more common in the higher dose groups (PF-06649751 3 mg, PF-06649751 6 mg and PF-06649751 9 mg treatment groups).

There were no notable findings in clinical laboratory. There appeared to be a small dose-related increase in heart rate without consistent changes in blood pressure (BP), except for the observations of orthostatic hypotension.

There was an increase of mean QTcF values in the higher dose groups (PF-06649751 6 mg and PF-06649751 9 mg) between 2 and 8 hours post dose, but no subject had a QTcF  $\geq 500$  msec or an increase of QTcF  $\geq 60$  msec.

To date, nausea and emesis have been identified as Adverse Drug Reactions (ADR) for PF-06649751.

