25. Screening supine blood pressure  $\geq 160$  mm Hg (systolic) or  $\geq 95$  mm Hg (diastolic), on a single measurement. If abnormal, up to 2 repeats are permitted following at least 5 minutes of rest. The screening value in that case will be the average of the 2 values closest to the normal range.
26. A decrease in systolic blood pressure (BP) of  $>20$  mmHg or in diastolic BP of  $>10$  mmHg measured 2 minutes after changing from a supine to standing position in the presence of symptoms of orthostasis. In the absence of symptoms of orthostasis a decrease in systolic blood pressure (BP) of  $>30$  mmHg or in diastolic BP of  $>15$  mmHg measured 2 minutes after changing from a supine to standing position (the mean of three independent sets of vital signs, taken at least 15 minutes apart at the screening visit, will determine eligibility).
27. 12-lead ECG (average of triplicate measures) demonstrating QTcF  $>450$  msec ( $>470$  msec for females) or a QRS interval  $>120$  msec at Screening.
28. Subjects with **ANY** of the following abnormalities in clinical laboratory tests at screening, as assessed by the study-specific laboratory and confirmed by a single repeat, if deemed necessary:
- Aspartate aminotransferase (AST)/serum glutamic oxaloacetic transaminase (SGOT) **or** alanine aminotransferase (ALT)/serum glutamic pyruvic transaminase (SGPT)  $\geq 2x$  upper limit of normal (ULN);
  - Total bilirubin  $\geq 1.5 x$  ULN; subjects with a history of Gilbert's syndrome may have a direct bilirubin measured and would be eligible for this study provided the direct bilirubin is  $\leq$  ULN.

29. A positive test for hepatitis B surface antigen or hepatitis C antibody.
30. A positive urine drug screen for drugs of abuse unless explained by medically indicated medication.

General and Administrative:

31. Subjects who are investigational site staff members directly involved in the conduct of the study and their family members, site staff members otherwise supervised by the investigator, or subjects who are Pfizer employees directly involved in the conduct of the study.
32. Participation in other studies involving investigational drug(s), or treatment with any investigational drug within 30 days (or as determined by the local requirement) or 5 half-lives preceding the first dose of study medication (whichever is longer).

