3.5.3. Vital Signs (Blood Pressure and Pulse Rate)

Blood pressure and pulse rate will be measured at times specified in the STUDY PROCEDURES section of this protocol. Subject temperature must also be assessed at Screening and Day 0 (Randomization) to confirm no symptoms of fever (see Exclusion Criteria #6). Additional collection times, or changes to collection times of blood pressure and pulse rate will be permitted, as necessary, to ensure appropriate collection of safety data.

Orthostatic hypotension is defined as a decrease of ≥ 20 mmHg for systolic blood pressure or ≥ 10 mmHg for diastolic blood pressure 2 minutes after standing from a supine position. Orthostatic hypotension may be symptomatic or asymptomatic.

Baseline will be the Day 0 measurement.

Determine if there is any blood pressure or pulse rate data abnormalities of potential clinical concern as defined in Pfizer Data Standards. This data will be determined Overall, and separately for Period A and Period B.

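### The any-post-baseline orthostatic hypotension row in SAP 6.6.3 cannot separate new cases from the pre-existing ones that the entry criteria allow

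*SAP*

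**What the plan says.** **Entry.** Protocol 4.2, Exclusion 26, sets two limits. With symptoms of orthostasis, a subject is excluded for "A decrease in systolic blood pressure (BP) of $>20$ mmHg or in diastolic BP of $>10$ mmHg". Without symptoms the limit is wider: "In the absence of symptoms of orthostasis a decrease in systolic blood pressure (BP) of $>30$ mmHg or in diastolic BP of $>15$ mmHg". Eligibility is judged once: "the mean of three independent sets of vital signs, taken at least 15 minutes apart at the screening visit, will determine eligibility".

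**Safety definition.** SAP 3.5.3 (and Protocol 7.2.5) defines orthostatic hypotension as a fall of at least 20 mmHg systolic or 10 mmHg diastolic two minutes after standing, and adds that "Orthostatic hypotension may be symptomatic or asymptomatic". The SAP baseline for vital signs is Day 0.

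**Analysis.** SAP 6.6.3 plans a non-standard table of subjects with orthostatic hypotension, "for each visit, last visit and any post-baseline incidence or orthostatic hypotension or minimum absolute change in postural blood pressure". It does not restrict, split or cross-tabulate by baseline status, and it plans no test or confidence interval for this table.

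**Comparable rules elsewhere in the SAP.** Under SAP 3.5.1 an adverse event is treatment emergent if "the event occurs for the first time during the effective duration of treatment and was not seen prior to the start of treatment", or if an earlier event became more severe. For the C-SSRS, SAP 3.5.7.1 defines new onset relative to baseline and ignores screening data, and SAP 6.6.7.1 uses subjects without suicidality at baseline as the denominator.

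**The concern.** The entry limits and the safety definition use different cut-offs, so a subject can be correctly enrolled and already be a case on the SAP's definition. If that subject meets the definition again at any later visit, the any-post-baseline row counts the subject together with someone whose pressure was normal at Day 0. The row is called an incidence, but it would not be one.

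This finding is relevant to the drug. Protocol 1.4.2 reports for the single-dose study in Parkinson's disease subjects (B7601009) a small dose-related rise in heart rate "without consistent changes in blood pressure (BP), except for the observations of orthostatic hypotension". It also lists one moderate, treatment-related case in the healthy-volunteer study B7601007. A reader of the final report will want to know, for each dose, how many subjects developed orthostatic hypotension on treatment and how many who already had it got worse. The planned row answers neither question.

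**Working it through.** **1. Who can enter and already be a case.** Set Exclusion 26 beside SAP 3.5.3:

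- Without symptoms: admitted if the systolic fall is at most 30 and the diastolic fall at most 15; a case if the systolic fall is at least 20 or the diastolic at least 10. The overlap is a systolic fall of 20 to 30 or a diastolic fall of 10 to 15, with neither entry limit exceeded.
- With symptoms: admitted at exactly 20 or exactly 10, because the entry rule uses a strict inequality and the definition does not.

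Eligibility rests on the mean of three sets at Screening, whereas the Day 0 vital signs are single (Protocol 6.2.1). A Day 0 reading can therefore meet the definition even when the Screening mean did not.

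**2. Would such subjects be counted again?** The Schedule of Activities has supine and standing pressure at Days 7, 28, 35, 70, 105 and 119, plus Days 14 and 21 if in clinic. If a baseline case meets the definition at each visit with probability 0.3 to 0.4, independently (my assumption), the chance of at least one hit in six visits is 1 − 0.7^6 = 88% to 1 − 0.6^6 = 95%. For subjects who enter the extension at Week 15 and skip Day 119, five visits give 1 − 0.7^5 = 83% to 1 − 0.6^5 = 92%. Recurrence could well be high.

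**3. What the row would show.** The plan states no figure for orthostatic hypotension, so there is none to reproduce. Arm sizes follow from the allocation ratios: 15 mg has 54 × 2/3 + 144 × 1/8 = 36 + 18 = 54; placebo has 54 × 1/3 + 144 × 1/8 = 18 + 18 = 36; each other dose has 144 × 2/8 = 36.

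Let b be the baseline prevalence, r the chance that a baseline case recurs, and p the new-onset rate in the rest. None of these is in the documents. The row shows b·r + (1 − b)·p in each arm. Assume p = 10% on placebo and 25% on active drug, with r = 100% in both. Among subjects free of the condition at baseline, the risk difference is 15.0 points and the risk ratio 2.50. The planned row would show:

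| b | Active | Placebo | Difference (points) | Ratio | Pre-existing share of active-arm cases |
|---|---|---|---|---|---|
| 5% | 28.75% | 14.5% | 14.25 | 1.98 | 17% |
| 10% | 32.5% | 19.0% | 13.5 | 1.71 | 31% |
| 20% | 40.0% | 28.0% | 12.0 | 1.43 | 50% |
| 30% | 47.5% | 37.0% | 10.5 | 1.28 | 63% |

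With r = 70% in both arms the ratio runs from 2.10 (b = 5%) to 1.38 (b = 30%).

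**4. The direction is not fixed.** In general the row's difference is (1 − b)(p1 − p0) + b(r1 − r0), with 1 for active and 0 for placebo. With equal recurrence it shrinks by the factor (1 − b). It exceeds the new-onset difference whenever r1 − r0 is larger than p1 − p0. With b = 20%, r0 = 50% and r1 = 80%:

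- active: 0.2 × 0.8 + 0.8 × 0.25 = 36%
- placebo: 0.2 × 0.5 + 0.8 × 0.10 = 18%
- difference: 18 points, against 15 for new onset.

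With new-onset rates of 10% and 35% the row shows 18% and 44%, a difference of 26 points against 25.

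**The case against.** Three points on the other side carry weight.

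*The comparison is not biased by imbalance.* Randomization balances baseline cases across arms in expectation. A reader might infer that the row dilutes the 15 mg signal. The documents do not support that: attenuation needs similar recurrence in all arms, it would apply to any active dose, and step 4 shows that it can reverse.

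*No inference is planned.* A reader might also infer a loss of power. SAP 6.6.3 plans no test or interval on this table, and SAP 6.6.1 describes safety analysis as generally exploratory, so a power figure would not describe this plan.

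*Baseline is not ignored everywhere.* SAP 6.6.3 has baseline and change-from-baseline summaries and a summary of postural change. The by-visit rows may include Day 0, since SAP 5.2 says each visit will be represented. Adverse events are handled as new or worsened. The SAP also reports some results without regard to baseline by design (laboratory abnormalities in 6.6.2, C-CASA categories in 6.6.7.1). Nor does it state that baseline cases are counted: it is silent, and such a subject counts only on meeting the definition again.

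These points limit the claim but do not close the gap. A Day 0 column gives a group rate, not which later cases are new. Group summaries of pressure do not classify subjects. Under Protocol 8.5 an abnormal finding becomes an adverse event only if it has symptoms, needs work-up or treatment, changes dosing, or is judged to be one, so an asymptomatic fall may never reach the adverse event tables.

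**Conclusion.** The point holds in a limited form. The threshold overlap follows directly from the two definitions. As written, the any-post-baseline row cannot separate new-onset from pre-existing or aggravated orthostatic hypotension in any arm. It may understate the difference from placebo for any active dose if baseline cases recur equally across arms. Under the assumptions in the table (5% to 30% baseline prevalence, full and equal recurrence) the difference would shrink by 5% to 30% of its value. Prevalence, recurrence and new-onset rates are all assumed, so neither size nor direction can be shown from the documents. No primary analysis or decision rule is affected. This is a cheap improvement to one descriptive safety table.

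**What to change.** In SAP 6.6.3:

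- Keep the all-subjects any-post-baseline row. Replacing it with a new-onset row would hide worsening in subjects who already had the condition.
- Add Day 0 prevalence of orthostatic hypotension by arm.
- Add a new-onset row whose denominator is subjects free of orthostatic hypotension at Day 0, the SAP's baseline. SAP 5.3 already falls back on the last pre-dose measurement when Day 0 is missing; state how triplicate Screening readings are classified in that case.
- Add a shift table of baseline against worst post-baseline status. A yes/no table would not show worsening, so use bands of postural fall, for example those the documents already use: below 20/10, from there up to 30/15, and above 30/15 mmHg.
- Correct the row's wording, where *or* stands between incidence and orthostatic hypotension and *of* appears to be meant.

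The entry criteria need no change for this purpose. All data are already collected. The cost is a few SAP sentences, one derived flag and one extra table. The new-onset row has a smaller denominator: at an assumed 20% baseline prevalence, about 54 × 0.8 = 43 subjects on 15 mg and 36 × 0.8 = 29 on placebo.
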